## 5. Study Population

Prospective approval of protocol deviations to recruitment and enrollment criteria, also known as protocol waivers or exemptions, is not permitted.

### 5.1. Inclusion Criteria

Participants are eligible to be included in the study only if all of the following criteria apply:

1. Participant must be in good health as determined by medical history, physical examination, vital signs, and investigator's judgment, including no known active pandemic infection.
2. Participant (healthy volunteers) has read and signed the study written ICF.
3. Male or female participant 22 to 65 years of age inclusive at screening.
4. Participant has clearly visible and palpable fat in the abdomen and flanks, and participant may also be assessed for visible and palpable fat in one or more of the following body areas: left and right lower aspects of the upper arms, left and right inner thigh, left and right outer thigh, or submental area, which in the investigator's opinion is appropriate for and may benefit from treatment.
5. Participant agrees to receive treatment of the abdomen and flanks (collectively, the midsection) and has option to receive treatment to at least 1 additional body area listed in criterion 4.
6. Participant has not had weight change fluctuations exceeding 5% of body weight in the preceding month.
7. Participant has a BMI of  $\geq 18.5$  and  $< 30$ . BMI is defined as weight in kilograms divided by height in meters squared ( $\text{kg}/\text{m}^2$ ).
8. Participant agrees to maintain weight (ie, within 5% of body weight) by not making any changes in diet or exercise routine during the course of the study.
9. Participant agrees to have photographs taken of the treatment area(s) during the scheduled time periods.

### 5.2. Exclusion Criteria

Participants are excluded from the study if any of the following criteria apply:

1. Participant has a history of an invasive fat reduction procedure (eg, liposuction, surgery, lipolytic agents, etc) within or adjacent to the area being considered for treatment.
2. Participant has implants (eg, breast implants) in or immediately adjacent to the area of intended treatment.
3. Participant has a history of prior surgery or scar tissue related to the area being considered for treatment.
4. Participant has a known history of cryoglobulinemia, cold urticaria, cold agglutinin disease, or paroxysmal cold hemoglobinuria.

5. Participant has a known sensitivity to cold or has any condition with a known response to cold exposure that limits blood flow to the skin, such as cold urticaria, Raynaud's disease, or chilblains (pernio).
6. Participant with a clinically significant bleeding disorder, or concomitant use of blood thinners, or is taking any medication that, in the investigator's opinion, may significantly increase the participant's risk of bruising or bleeding. Participant on low dose aspirin for medical condition is excluded if the medical history suggests significant risk of bruising or bleeding per investigator's clinical judgement.
7. Participant has a history of carpal tunnel syndrome, compartment syndrome, or deep vein thrombosis in the upper or lower extremities (only applicable for participants receiving treatment to the upper arms or thighs).
8. Participant is currently taking or has taken diet pills or weight control supplements within the past 6 months.
9. Participant has any skin conditions, such as moderate to excessive skin laxity, open wound, or scars, and active infection, eczema, dermatitis or rashes in the location of the treatment sites that may interfere with the treatment or evaluation (stretch marks are not an exclusion).
10. Participant has an active implanted device such as a pacemaker, defibrillator, drug delivery system, or any other metal-containing implant, within or adjacent to the area being considered for treatment.
11. Participant (WOCBP) is pregnant or intending to become pregnant in the next 3 to 6 months and does not agree to use reliable contraception during the study.
12. Participant is lactating or has been lactating in the past 6 months.
13. Participant is unable or unwilling to comply with the study requirements.
14. Participant is currently enrolled in a clinical study of any unapproved investigational device, investigational product, or any other type of medical research judged not to be scientifically or medically compatible with this study.
15. Participant has any other condition or laboratory value that would, in the professional opinion of the investigator, potentially affect the participant's response or the integrity of the data or would pose an unacceptable risk to the participant.
16. Participant has had a non-invasive fat reduction and/or body contouring procedure in the area(s) of intended treatment within the past 12 months.
17. Participant needs to administer, or has a known history of subcutaneous injections, into the area(s) of intended treatment (eg, cortisone, heparin, insulin) within the past 6 months.
18. Participant with known sensitivity or allergy to fructose, glycerin, isopropyl alcohol, or propylene glycol.
19. Participant has impaired peripheral circulation in the area to be treated.
20. Participant has neuropathic disorders such as post-herpetic neuralgia or diabetic neuropathy.

21. Participant has impaired skin sensation in or immediately adjacent to the treatment area(s).
22. Participant has a history of hernia in or immediately adjacent to the treatment area(s).
23. Participant diagnosed with a systemic fibrosing disease or fibrosis in the area intended or adjacent to the area to be treated.

### **5.3. Lifestyle Considerations**

Lifestyle considerations are not applicable to this study.

### **5.4. Screen Failures**

Screen failures are defined as participants who consent to participate in the clinical study but are not subsequently entered in the study. A minimal set of screen failure information is required to ensure transparent reporting of screen failure participants to meet the CONSORT publishing requirements and to respond to queries from regulatory authorities. Minimal information includes demography, screen failure details, eligibility criteria, and any AE.

## 6. Study Intervention

Study intervention is defined as the medical device (CoolSculpting Elite System and CoolSculpting Elite applicators) intended to be administered to a study participant according to the study protocol.

### 6.1. Study Intervention Administered (CoolSculpting Elite System)

Participants will undergo a CoolSculpting Elite treatment in an outpatient clinical setting. A treatment is comprised of timed segments of cooling (treatment cycle) followed by 2 minutes of manual massage. Treatments will be administered according to the CoolSculpting Elite user manual that has been prepared for specific countries and provided to the study sites. All device deficiencies (including malfunction and use error) shall be documented and reported by the investigator throughout the clinical investigation (see Section 8.3.8) and appropriately managed by the sponsor.

#### 6.1.1. Identity of the CoolSculpting Elite System

The CoolSculpting Elite System is a portable thermoelectric cooling and heating device that applies controlled cooling or heating to a treatment site on the participant's skin. The system has two umbilicals attaching the applicators to the control unit to allow dual applicator use at the same time. The system is comprised of a control unit, applicators, and supplies such as cards, gelpads, pretreatment skin wipes, liners, foam borders, securement grip, support arm and comfort straps. The applicators, gelpads, pretreatment skin wipes, liners, foam borders, and comfort straps are parts applied to patient. During a treatment, the operator applies a gelpad and applicator to the patient's skin. For a treatment where two or more applicators are used simultaneously, additional applicators are applied with another gelpad. The applicator(s) draw tissue into the applicator cup(s) and hold(s) the tissue against the cooling surfaces of the applicator(s). The operator then starts the treatment. The Surface S150 applicator does not draw in tissue and does not have a cup. The treatment card (can be referred to as "Standard" card or "SOLO" card depending on country) provides treatments and profiles for use with the system.

During the cooling treatment, sensors in the cooling surfaces of the applicator(s) monitor the skin surface and provide feedback [REDACTED]. The gelpad(s) protect the skin by providing thermal coupling at the interface between the cooling surfaces of the applicator(s) and the skin.

The CoolSculpting Elite System operates applicators at temperatures below 0°C. Therefore, the system monitors tissue during cooling and employs multiple safety features, including the Freeze Detect system, to minimize the risk of damage to tissue. In spite of these multiple safety features, on rare occasions, a possible freeze condition may occur that can be detected by the Freeze Detect System.

[figure not shown]
The Freeze Detect system is comprised of several features, including thermal sensors and proprietary algorithmic software. Freeze Detect is an integral part of the CoolSculpting System and is automatically employed when a treatment is initiated. When the Freeze Detect system detects a possible freeze condition, it stops the treatment and displays a Z409 message. If this message is received, remove the applicator and gel pad or gel, and assess the tissue before taking further action. The current recommended practice is to wait at least 24 hours before retreating the

area relating to a Z409 error message. Failure to follow instructions could result in injury to the participant, including first- or second-degree burns. Second-degree burns or complications of second-degree burns may result in hyper- or hypopigmentation.

### 6.1.2. Control Unit

The control unit is shown in Figure 6-1. For additional detail, please see the CoolSculpting Elite System user manual.

**Figure 6-1** CoolSculpting Elite Control Unit

- (A) Touchscreen display: The touchscreen displays system controls, information about the status of the system, information about the treatment, and messages for the operator. You can rotate or tilt the display to accommodate better access.
- (B) Card Slot: The card slot accepts treatment cards. You must insert an appropriate SOLO treatment card with active treatments in order to begin the procedure.
- (C) Casters and locks: The control unit has four casters that swivel. Each caster has a lock. Always engage all four caster locks when the unit is stationary. Disengage the caster locks to move the unit.
- (D) Bucket: The bucket is a storage area for applicators and/or consumables. You can remove the bucket from the control unit for cleaning.
- (E) Top cap lip: When the applicator is resting on top of the control unit, the top cap lip helps keep the applicator in place.
- (F) Access panel: The access panel covers vents, a USB port, and the chiller tank cap.

- (G) Power receptacle and power switch: The power receptacle houses the plug for the power cord. The power switch controls the power to the control unit and system components. Contact customer service if the power entry mode appears to be broken.
- (H) Connector ports for umbilical cords for applicators A and B: The control unit has two connector ports where two umbilical cords attach to perform a simultaneous treatment. Simultaneous treatment is an option, but not necessary.
- (I) Vents: Vents provide airflow that reduces heat build-up inside the control unit. Ensure that all vents are free from obstructions when the control unit is in operation.
- (J) Soft power button: The display includes a soft power button at the lower right corner, which is used to power on the system, after turning the power switch on the rear of the system to the “On” position. The soft power button may also be used to power off the system.

### 6.1.3. Applicators

The applicator delivers controlled cooling to the treatment site. The applicator consists of the applicator connector, the applicator cable, and the applicator head. The applicator is used with supplies provided by the sponsor.

Always use gelpads with the applicator. The applicators are designed to treat most body areas. Investigators should consider all physical aspects of the area to be treated and use the applicator that will fit best for each participant and body area being treated.

The CoolSculpting Elite applicators available in this study depend on country clearances and can include Curve 240, Curve 150, Curve 120, Flat 165, Flat 125, Surface 150, and Curve 80.

For additional details regarding applicators, please see the CoolSculpting Elite user manual.

## 6.2. Additional Study Intervention Supplies

The following supplies will be provided to support use of the CoolSculpting Elite System:

- Card: Provides treatment cycles and profiles for use with the system
  - Profiles define the number of timed segments of cooling
  - Each treatment cycle provides a single treatment
- Coolant: The control unit requires an adequate supply of coolant (from the manufacturer). When the coolant level is low, the system displays a recoverable exception message.
- Gelpad: Provides thermal contact between the applicator and the participant’s skin and mitigates minor variances in device-to-skin contact (note: this is a single-use item; use a new gelpad for each treatment).
- Gel trap: Fits into the slot of the applicator and prevents the ingress of gel into the vacuum system (note: this is a single-use item, use a new gel trap for each treatment).
- Pretreatment skin wipe: Use the pretreatment skin wipe to prepare the treatment site before applying a gelpad (note: this is a single-use item; use a new pretreatment skin wipe for each treatment).

- Securement system: minimizes movement of the applicator during treatment.
- Liner (applies to Surface 150 applicator only): provides an interface between the gelpad and applicator.
- Foam border (applies to Surface 150 applicator only): minimizes movement of the surface applicator during treatment.
- Securement grip (applies to Surface 150 applicator only): minimizes movement of the surface applicator during treatment.
- Support arm (applies to Curve 80 applicator only): intended for use in supporting the C80 applicator head during treatment.

For additional details, please see the CoolSculpting Elite user manual.

### **6.3. Randomization and Blinding**

Blinding is not applicable to this open-label, nonrandomized study. Blinding will only be employed for photograph review by an independent panel of physician reviewers with expertise in the areas of dermatology and/or plastic surgery.

At screening, after the participant has signed the ICF, the participant will be assigned a participant number sequentially based on the order in which the participant is screened into the study. This participant number will serve as the participant identification number on all study documents.

### **6.4. Study Intervention Compliance**

When participants are treated at the study site, they will receive study intervention directly from the investigator or designee, under medical supervision. The date and time of each treatment session administered in the clinic will be recorded in the source documents and the eCRF.

The study investigators are responsible for performing the study in compliance with the protocol. Non-adherence to the protocol is to be classified as a protocol violation or protocol deviation, as defined below.

#### **Protocol Violation**

A violation is any non-adherence to the protocol that may result in significant additional risk to the participant (eg, enrollment of a participant who does not meet the study criteria). A protocol violation can also be an event of non-adherence to GCPs that may impact participant safety (eg, failure to obtain proper consent before performing study procedures). Violations should be reported to the study sponsor and the IRB within 5 working days if they occur.

#### **Protocol Deviation**

A deviation is any non-adherence to study procedures that does not result in additional risk to the participant (eg, participant missed a visit). Protocol deviations are not required to be reported to the IRB; however, they must be recorded on the study eCRFs and may be reported and reviewed in conjunction with the progress report as part of the annual review process.

## 6.5. Concomitant Therapy

All concomitant medications including vaccinations and procedures will be recorded on the eCRFs. Concomitant medications that are part of routine care are allowed and can be used during the study.

### 6.5.1. Prohibited Therapy

Diet pills or weight control supplements are not permitted (see Section 5.2, exclusion criterion # 8). Concomitant use of blood thinners, or any medication or dietary supplement that increases the risk of bruising such as fish oil, garlic, ginkgo, and vitamin E are not permitted. Participant on low dose aspirin for medical condition is excluded if the medical history suggests significant risk of bruising or bleeding per investigator's clinical judgement. Concomitant use of surgical or nonsurgical fat reduction or body contouring procedures (eg, radiofrequency lipolysis, low-level laser therapy, high-intensity focused ultrasound, electromagnetic muscle stimulation) or injectable lipolytic agents during the course of the study are not permitted (see Section 5.2, exclusion criterion #1, 16).

Additionally, at the discretion of the investigator, any topical creams or other medications that may impact the safety or effectiveness of the treatment are not permitted.

## 6.6. Dose Modification

For this device, the term "dose" refers to a CoolSculpting Elite treatment cycle. One or more treatment cycles will be delivered at the investigator's discretion at each treatment session. Treatment cycles can be delivered simultaneously or sequentially at investigator discretion during a treatment session. Study site investigators will administer up to 2 treatment sessions to the treatment areas in accordance with the CoolSculpting Elite System User Manual.

All participants entered into the study will receive a CoolSculpting treatment session (Visit 2) for the body areas selected for treatment. A participant may receive an additional treatment session at Visit 6 for body areas that were treated at Visit 2 as determined by the investigator.

Guidance for the recommended/required range of treatment sessions and treatment cycles by body area, and overall, is presented in Table 6-1.

**Table 6-1 Guidance for Number of Treatment Sessions and Treatment Cycles Per Body Area**

Body Area	Minimum Number of Treatment Sessions	Maximum Number of Treatment Sessions	Maximum Number of Treatment Cycles Per Treatment Session	Maximum Total Number of Treatment Cycles
Abdomen and flanks (Midsection)	1	2	8	16
Upper Arms (inclusive of both left and right arm)	0	2	4	8
Inner Thighs (inclusive of both left and right inner thigh)	0	2	4	8
Outer Thighs (inclusive of both left and right outer thigh)	0	2	4	8
Submental	0	2	2	4

## **6.7. Intervention after the End of the Study**

There is no intervention planned after the end of the study.

## 7. Discontinuation of Study Intervention and Participant Discontinuation/Withdrawal

A premature discontinuation will occur if a participant who signs the ICF and receives study intervention ceases participation in the study, regardless of circumstances, before the completion of the protocol-defined study procedures.

Notification of early participant discontinuation from the study and the reason for discontinuation will be made to the sponsor and will be clearly documented on the appropriate eCRF.

Reasons for discontinuation from the study intervention and/or the study may include the following commonly used or other acceptable terms:

Commonly Used Terms	Other Acceptable Terms
Adverse event	Death
Lost to follow-up	Disease relapse
Other	Progressive disease
Physician decision	Technical problems
Pregnancy	
Protocol deviation	
Screen failure	
Site terminated by sponsor	
Study terminated by sponsor	
Withdrawal by participant	

### 7.1. Discontinuation of Study Intervention

During the treatment, study intervention may be discontinued due to significant discomfort, wellness issues, psychological issues, or the participant's refusal to continue the treatment.

### 7.2. Participant Discontinuation/Withdrawal from the Study

- A participant may withdraw from the study at any time at his/her own request, or may be withdrawn at any time at the discretion of the investigator for safety, behavioral, compliance, or administrative reasons. This is expected to be uncommon.
- At the time of discontinuing from the study, if possible, an early discontinuation visit should be conducted. The following data should be collected at the time of study exit and follow-up and for any further evaluations that need to be completed:
  - Date of discontinuation from the study
  - Reason for discontinuation/withdrawal from the study
  - Date of study completion, if applicable

- If discontinued due to AE or device deficiency, complete the relevant eCRF and SAE/Device forms
- If discontinued due to pregnancy, complete the Pregnancy form
- Clinical assessment of treated areas for potential AEs.
- Participants withdrawing from the study will be encouraged to complete the same final evaluations as participants completing the study according to this protocol, particularly safety evaluations. The aim is to record data in the same way as for participants who completed the study.
- The participant will be permanently discontinued both from the study intervention and from the study at that time.
- If the participant withdraws consent for disclosure of future information, the sponsor may retain and continue to use any data collected before such a withdrawal of consent.
- During the course of the study, it may be necessary to employ mitigation strategies to enable the investigator to ensure participant safety and continuity of care. Acceptable mitigation strategies are identified and included in Section 8.

The investigator should contact the sponsor before discontinuing a participant from the study for a reason other than "planned per protocol," to ensure all acceptable mitigation steps have been explored.

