**Table 2-2      Reported Adverse Events**

Adverse Events	Description
First-degree burn	Skin damage from burns may be due to hot or cold. A first-degree burn is superficial and causes local inflammation of the skin. The inflammation is characterized by pain, redness, and mild swelling. The skin may be very tender to touch.
Second-degree burn	Second-degree burns are deeper and, in addition to the pain, redness, and inflammation, there is also blistering of the skin.
Third-degree burn	Third-degree burns are deeper still, involving all layers of the skin. Because the nerves and blood vessels are damaged, third-degree burns appear white, leathery, and tend to be relatively painless.
Severe pain	Patients may experience pain of varying severity, which more commonly can be described as mild to moderate, and in rare instances, can be severe.
Cold-induced panniculitis	Severe inflammation which requires medical or surgical intervention.
Skin pigment changes	The appearance of hyperpigmentation or hypopigmentation in the treatment area.
Infection	Infection at the treatment site, diagnosed by a physician and requiring medical intervention.
Vasovagal symptoms	The occurrence of symptoms of anxiety, light-headedness, dizziness, nausea, sweating, near-syncope, or syncope (fainting).
Allergic/irritant contact dermatitis	Itchy rashes and skin peeling that may result from prolonged exposure to gel pad or applicator pressure
Subcutaneous induration	Hardness within the treatment area, either as general firmness or discrete nodules.
Paradoxical adipose hyperplasia	Visibly enlarged tissue volume within the treatment area which may become evident 2-5 months after treatment.
Hernia	Creation or exacerbation of hernia. Hernia is defined as a protrusion of an organ or the fascia of an organ through the wall of the cavity that normally contains it.
Treatment area demarcation	Treatment area demarcation: excessive fat removal in the treatment area causing unwanted indentation.
Other	Any other untoward medical event determined by the investigator to be an AE, regardless of the relationship to the device or treatment.

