## 4. Study Design

### 4.1. Overall Design

This is a global, multicenter, multi-country, prospective, open-label, nonrandomized, interventional cohort, medical device post-marketing study evaluating the use of CoolSculpting Elite and CoolSculpting Elite applicators for noninvasive subcutaneous fat reduction of the abdomen, flanks, upper arms, inner thighs, outer thighs, and/or submental area in healthy volunteers. Participants will be enrolled at approximately 9 study sites.

Participants are eligible to receive up to two treatment sessions separated 8 weeks apart for the body areas eligible for treatment. Assessments will be completed 12 weeks after the final treatment session.

- If a participant receives only one treatment session for specific body area(s), the participant will return at Visit 8 for the 12-week post-treatment session 1 follow-up assessment and study exit.
- If a participant receives two treatment sessions for specific body area(s), the participant will return at Visit 9 for the 12-week post-treatment session 2 follow-up assessment and study exit.
- If a participant receives only one treatment session to a specific body area and two treatment sessions to another specific body area, the participant will return for both 12-week follow-up visits: Visit 8 for the 12-week post-treatment session 1 assessment of the body area that received only one treatment session and Visit 9 for the 12-week post treatment session 2 assessment of the body area receiving two treatment sessions; Visit 9 will also be the study exit visit for this participant.

Participant body areas selected for treatment during the study must be treated during the first treatment visit (Visit 2) and no new body areas may be treated at Visit 6. Participants planning to receive only one treatment session to a specific body area must have this treatment in Visit 2 during the first treatment session. Per investigator discretion, body areas identified for treatment may be treated simultaneously or sequentially. If sequential or simultaneous treatment is performed, there will be no difference in other treatment activities. Skin preparation, pain assessment, treatment site assessment, and post-massage, etc. will be identical in either case.

The study duration is up to approximately 20 weeks and consists of up to 7 scheduled study visits and 2 phone follow-ups per participant:

- Visit 1 (screening, Days -7 to 1)
- Visit 2 (treatment session #1, Day 1 + 3 days)

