### **8.3.8.2.      Follow-up of Medical Device Deficiencies**

- AEs resulting from medical device deficiencies will be followed up.
- Follow-up applies to all participants, including those who discontinue study intervention or the study.
- The investigator is responsible for ensuring that follow-up includes any supplemental investigations as indicated to elucidate the nature and/or causality of the deficiency.
- New or updated information will be recorded on the originally completed form with all changes signed and dated by the investigator.

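### Section 7.2 ends study participation at withdrawal without securing the 12-week safety and satisfaction data, and Section 7.1 does not say that a participant who stops treatment stays in follow-up

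*Protocol*

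**What the plan says.** Under Protocol Section 7.2 a participant may leave at their own request, or "may be withdrawn at any time at the discretion of the investigator for safety, behavioral, compliance, or administrative reasons". The section adds "This is expected to be uncommon" and gives no number. The consequence is stated in one bullet: "The participant will be permanently discontinued both from the study intervention and from the study at that time".

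The same section contains safeguards. "At the time of discontinuing from the study, if possible, an early discontinuation visit should be conducted". It calls for a clinical assessment of the treated areas. "Participants withdrawing from the study will be encouraged to complete the same final evaluations as participants completing the study according to this protocol", with emphasis on safety evaluations (repeated in SAP Section 1.0). It asks the investigator to contact the sponsor before discontinuing a participant.

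Section 7.1 covers stopping treatment during a session and is silent on what follow-up then applies. On exposure, Section 4.1 says "Participants are eligible to receive up to two treatment sessions separated 8 weeks apart".

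The primary analysis set (Protocol Section 9.3, Evaluable Population 1 in SAP Section 4.0) needs a completed midsection plan and the 12-week CSQ-Midsection Item 1. The SAP also excludes significant deviations or violations. It imputes nothing (Section 9.2) and plans no sensitivity analysis of the primary endpoint (Section 9.3.3).

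**The concern.** With at most two sessions, there comes a point for every participant when no study treatment remains to be withheld. Withdrawal after that point removes only observation. Before that point, the decision to treat no further and the decision to stop observing are different decisions. Section 7.2 has no route by which someone withdrawn for safety or compliance is kept in the visits already on the schedule.

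Two things are at stake. The first is safety information that becomes visible only with time. Table 2-2 describes paradoxical adipose hyperplasia as "Visibly enlarged tissue volume within the treatment area which may become evident 2-5 months after treatment", and Table 2-1 counts sensory change as prolonged only beyond 12 weeks. The second is the primary endpoint. The study is open-label and single-arm, so a withdrawal decision made by an investigator who knows how the participant is doing can be related to the outcome, and anyone without the 12-week answer leaves the denominator.

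**Working it through.** **The plan's own figure.** Inputs from Protocol Section 9.2: n = 96, satisfaction rate 63.9%, exact 95% interval of width 0.2, attrition 12%. Clopper-Pearson limits are the 2.5% quantile of Beta(x, n − x + 1) and the 97.5% quantile of Beta(x + 1, n − x). With x = 0.639 × 96 they are 0.5346 and 0.7346, a width of 0.2000 (0.2010 at n = 95). Then 96 / (1 − 0.12) = 109.1, rounded up to 110. The plan's figures reproduce. The planned loss is 110 − 96 = 14.

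**Obligations that survive exit.**

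- Recorded SAEs: followed to resolution, stabilization, explanation or loss to follow-up (Section 8.3.3).
- Recorded AEs: followed until resolved, stabilized or judged chronic (Section 10.5.4).
- AEs from device deficiencies: followed even in those who have left (Section 8.3.8.2).
- New events after participation ends: not actively sought. The investigator must notify the sponsor of a related SAE only on learning of it (Section 8.3.1).
- Numbness or tingling present at an early exit: an anticipated effect, not an AE, unless severe or lasting beyond 12 weeks (Section 2.3.2, Table 2-1). Section 4.1 schedules extra calls when such effects are reported at the one-week contact, but does not say these continue after withdrawal.
- 12-week CSQ-Midsection: no obligation beyond encouragement, and no date.

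The last three items are the gap.

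**Time not observed, by example.** A participant with one session who leaves at Visit 4 (Day 28) and has no later contact misses 84 − 28 = 56 days, or 8 of the 12 weeks. With 365 / 12 = 30.4 days to a month, Visit 8 (Day 84 + 14) falls at 84 / 30.4 = 2.8 to 98 / 30.4 = 3.2 months. Staying to Visit 8 therefore recovers about 0.8 to 1.2 months of the three-month span from month 2 to month 5. Participants who complete the study after one session are not observed for the rest either.

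**Bounds on the satisfaction rate.** The documents do not say how many participants would be withdrawn or how they would have answered, so both are assumptions. If s of 96 are satisfied and m are missing, of whom k would have been satisfied, the rate over all is (s + k) / (96 + m), with k from 0 to m. Two values of s are used: 61, close to the planning rate (0.639 × 96 = 61.3), and 86, matching the 89.6% of the earlier study described in Section 2.2. The two values of m are 3, for uncommon withdrawal, and 14, the whole planned loss.

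| s/96 | m | all missing dissatisfied | all missing satisfied | largest overstatement |
|---|---|---|---|---|
| 61/96 = 63.5% | 3 | 61/99 = 61.6% | 64/99 = 64.6% | 1.9 points |
| 61/96 = 63.5% | 14 | 61/110 = 55.5% | 75/110 = 68.2% | 8.1 points |
| 86/96 = 89.6% | 3 | 86/99 = 86.9% | 89/99 = 89.9% | 2.7 points |
| 86/96 = 89.6% | 14 | 86/110 = 78.2% | 100/110 = 90.9% | 11.4 points |

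For scale, the planned half-width is 0.2 / 2 = 10 points. At 89.6% and n = 96 the exact interval has width 0.1321, a half-width of 6.6 points. The rows with m = 14 are outer limits for all attrition, not estimates of what Section 7.2 causes.

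**The case against.** The other side has a good deal to stand on.

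The quoted bullet sits under withdrawal from the study. It says that whoever leaves the study also leaves treatment, not that whoever stops treatment must leave. Section 7 speaks of discontinuing the intervention and/or the study, and Section 8 treats continuing or stopping the intervention as its own question. Session 2 is optional at the investigator's decision, and participants with one session go on to Visit 8. An investigator can therefore already give no second session and keep the participant. This stands; what is missing is a sentence saying so.

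A reader might infer that follow-up simply stops and safety data are lost. The documents do not support that. The exit visit, the assessment of treated areas, the prior contact with the sponsor and the follow-up of recorded events are all planned, and the timing of the encouraged evaluations is left open, not fixed at the day of leaving.

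A reader might also infer that the participants lost are those with the worst results. Safety is one of four listed investigator reasons. Behavioral, compliance and administrative reasons, or a participant's own request, need not mean a poor outcome, and withdrawal is expected to be uncommon.

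A third tempting reading is that Section 7.2 contradicts Section 8.3.8.2, which says "Follow-up applies to all participants, including those who discontinue study intervention or the study". That sentence concerns device deficiencies and the AEs arising from them. Following such an event after someone leaves is compatible with Section 7.2.

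Finally, the study is descriptive and tests no hypothesis. That lowers the stakes, but the satisfaction rate and its interval are the main result, and selective loss affects them all the same.

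**Conclusion.** The point holds as a gap in the protocol. At withdrawal the text ends participation without requiring the 12-week safety assessment or CSQ-Midsection, and Section 7.1 leaves the follow-up of those who stop treatment unstated. Applied as written, this can lose new late events, anticipated effects that become AEs only when prolonged, and the primary endpoint answer, in a way that may depend on outcome.

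The size is unknown. Under the assumption that every missing participant was dissatisfied, the overstatement is about 2 points for 3 missing and about 8 points for 14 when 61 of 96 are satisfied (about 3 and 11 points at 86 of 96). If the missing participants were satisfied, the reported rate would be too low instead. These figures should not be read as the bias that Section 7.2 produces. Part of the loss also belongs to the SAP: a participant who did not complete the midsection plan, or who has a significant deviation, is outside Evaluable Population 1 even with a 12-week answer.

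The change is worth making because an analysis plan can be amended later, while data that were never collected cannot be recovered.

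**What to change.** - In Sections 7.1 and 7.2, state that a decision to give no further treatment, left to the investigator as now, is recorded as discontinuation of intervention only. The participant then stays in the visits already scheduled through 12 weeks after the last treatment received, including AE assessment and the CSQ, unless consent is withdrawn, the participant is lost to follow-up or follow-up is not possible.
- Reword the bullet that ends participation so that it agrees with the bullet on completing the same final evaluations, and give those evaluations a time relative to the last treatment.
- Reconcile the new wording with Section 10.4.3, which discontinues from the study any participant who becomes pregnant.
- In the SAP, add a supplementary analysis of the primary endpoint in all treated participants, with bounds for missing answers as in the table above. Without it, the answers of participants with an incomplete midsection plan or a significant deviation are collected but not analysed for the primary endpoint.

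The cost is protocol wording and one extra SAP table. No new visits are created; a few participants attend visits that they would otherwise skip.
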